12.7 Follow-up Procedures for Adverse Events

The Investigator may be asked to provide follow-up information to the GW PVD for any AEs reported.

AEs considered related to the IMP by the Investigator or the Sponsor should be followed up until resolution or the event is considered stable.

It will be left to the Investigator's clinical judgment whether or not an AE is of sufficient severity to require the patient's removal from treatment. A patient may also voluntarily withdraw from treatment due to what he or she perceives as an intolerable AE, further details of withdrawal are presented in [Section 10](#). If either of these occurs, the patient must undergo an end of treatment assessment and be given

appropriate care under medical supervision until symptoms cease or the condition becomes stable.

12.8 Potential Cases of Drug-Induced Liver Injury

All investigational centers are required to submit to the GW PVD the laboratory results for any patient after randomization that meet the criteria for the selected laboratory parameters as follows:

- ALT or AST $> 3 \times$ ULN **and** (TBL $> 2 \times$ ULN **or** INR > 1.5).
- ALT or AST $> 3 \times$ ULN with the appearance of fatigue, nausea, vomiting, right upper quadrant pain or tenderness, fever, rash, and/or eosinophilia ($> 5\%$).
- ALT or AST $> 8 \times$ ULN.
- ALT or AST $> 5 \times$ ULN for more than 2 weeks.

These reports must be sent to the GW PVD using the same fax number for SAE reporting within 24 hours of becoming aware of the results. In addition, please send a copy of the patient's baseline laboratory results with all reports to GW PVD.

Abnormal values in AST and/or ALT concurrent with abnormal elevations in TBL that meet the criteria outlined above are considered potential cases of drug-induced liver injury and will be considered as protocol defined criteria for withdrawal and important medical events. The Investigator will arrange for the patient to return to the investigational site as soon as possible (within 24-48 hours of notice of abnormal results) for repeat assessment of ALT, AST, TBL, alkaline phosphatase and gamma glutamyl transferase, detailed history and physical examination. Patients should be followed in this way until all abnormalities have normalized (in the Investigator's opinion) or returned to the baseline state; however, if the above transaminase elevation criteria are confirmed by the first set of follow-up laboratory tests, the patient must be withdrawn from the trial.

Elevations in ALT or AST $> 3 \times$ ULN **or** TBL $> 2 \times$ ULN alone are not considered potential cases of drug-induced liver injury, but will be followed as detailed above, within 72 hours' notice of abnormal results. If the patient cannot return to the investigational site, repeat assessments may be done at a local laboratory and the results sent to GW PVD.

12.9 Notification of Safety Information to Investigators, Regulatory Authorities and Ethics Committees

In accordance with the EU Clinical Trials Directive⁷⁷, relevant parts of the FDA Code of Federal Regulations⁷⁸ and any national regulations, GW will inform Investigators, regulatory authorities and relevant IRB/ECs of all relevant safety information. This will include the reporting of relevant SAEs and all Suspected Unexpected Serious Adverse Drug Reactions (SUSARs).

This information will be provided through 3 sources:

- 1) IB⁷¹: a compilation of the clinical and non-clinical safety data available on the IMP that is relevant to the study on the IMP in human patients. The IB is updated annually.
- 2) Development Core Safety Information: this document actually forms the Safety Section of the IB⁷¹, or is updated as an appendix of the IB⁷¹. This document is revised if necessary, when new important safety information becomes available (potentially up to a few times a year).
- 3) Council for International Organizations of Medical Sciences (CIOMS) reports: these reports are issued every time a SUSAR is reported to GW. They provide information on individual case reports and are sent to all the regulatory authorities, the relevant central IRB/ECs which have approved the study and Investigators. As required, the Investigator should notify their regional ECs of SAEs or SUSARs occurring at their site and other AE reports, i.e., CIOMS reports and any additional safety documentation received from GW, in accordance with local procedures.

In the USA, Investigators are normally required to promptly report to their IRBs all unanticipated problems involving risks to human patients, or others, including AEs that should be considered unanticipated problems. Based on current FDA guidance⁷⁴ the following clarification is provided in determining what constitutes an unanticipated problem:

In general, an AE observed during the conduct of a study should be considered an unanticipated problem involving risk to human patients, and reported to the IRB, *only* if it were unexpected, serious, and would have implications for the conduct of the study (e.g., requiring a significant, and usually safety-related, change in the protocol such as revising inclusion/exclusion criteria or including a new monitoring requirement, informed consent/assent, or IB). An individual AE occurrence *ordinarily* does not meet these criteria because, as an isolated event, its implications for the study cannot be understood.

The FDA guidance⁷⁸ states that, accordingly, to satisfy the Investigator's obligation to notify the IRB of unanticipated problems, any Investigators participating in a

multicenter study may rely on the Sponsor's assessment and provide to the IRB a report of the unanticipated problem prepared by the Sponsor.

GW will inform Investigators (regulatory authorities and applicable IRB/ECs) of any safety issues or case reports that are considered to be unanticipated and provide such reports as mentioned above. It should be noted that a single SUSAR report notified to Investigators in the study does not necessarily constitute an unanticipated problem unless identified by GW in the submission cover letter.

As a minimum, the recipient will be sent all of the above and relevant updates between the period from ethical approval and final database lock.

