Urea (blood urea nitrogen [BUN])			

Investigators at study centers will be notified of safety laboratory test results. All laboratory results will be reviewed and the reports signed by an Investigator. Any results considered to be of clinical significance must be addressed and followed up as clinically appropriate. See [Section 12.8](#) for guidance on evaluation of potential drug-induced liver injury. All laboratory results considered to represent an AE must be documented on the CRF.

Repeat samples will be taken, if required, for clinical follow-up or if the sample is lost or damaged. Any abnormal end of treatment clinical laboratory result of clinical significance must be repeated at regular intervals until it returns to normal, or until an Investigator is satisfied that the abnormality is not related to the IMP and needs no further investigation.

Sample volume requirements and processing procedures will be detailed in a separate laboratory manual. The patient/caregiver must be advised that it may not be safe for the patient to undertake further blood tests within one month of any study-related blood draws and to inform the Investigator if they suffered any blood loss during the one-month period leading up to a planned blood draw.

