10 WITHDRAWAL

In accordance with the Declaration of Helsinki⁷³, the FDA regulations relating to good clinical practice (GCP) and clinical trials^{74,75,76}, the EU Clinical Trials Directive 2001/20/EC⁷⁷ and/or other applicable regulations, a patient has the right to withdraw from the study at any time and for any reason without prejudice to his or her future medical care by the physician or at the institution.

The patient must be withdrawn from the study if any of the following apply:

- Administrative decision by the Investigator, GW, or a Regulatory Authority.
- Pregnancy.
- Protocol deviation that is considered to potentially compromise the safety of the patient.
- Withdrawal of patient consent/assent.
- Withdrawal of parent(s)/legal representative consent.
- Lost to follow-up.
- ALT or AST > 3 × ULN **and** (TBL > 2 × ULN **or** INR > 1.5).
- ALT or AST > 3 × ULN with the appearance of fatigue, nausea, vomiting, right upper quadrant pain or tenderness, fever, rash, and/or eosinophilia (> 5%).
- ALT or AST > 8 × ULN.
- ALT or AST > 5 × ULN for more than 2 weeks.

Note: Prior to withdrawal for the transaminase elevations noted above, the Investigator may choose to confirm the transaminase elevations by repeating the following laboratory tests within 24 to 48 hours: ALT, AST, TBL, INR, % eosinophils, gamma glutamyl transferase and alkaline phosphatase. **Should the above transaminase elevation criteria be confirmed, the patient must be withdrawn from the trial.**

Patients may also be withdrawn from the study for any of the following:

- Patient non-compliance.
- AE which, in the opinion of the Investigator, would compromise the continued safe participation of the patient in the study.
- Any evidence of drug abuse or diversion.
- Suicidal ideation or behavior of type 4 or 5 during the treatment period, as evaluated with the C-SSRS.

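### Protocol 12.8's repeat liver panel omits INR and % eosinophils, which Section 10 and the synopsis name for the same four withdrawal criteria

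*Protocol*

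**What the plan says.** Protocol 12.8 lists four liver criteria, and Section 10 and the synopsis (Criteria for Withdrawal) list the same four as mandatory withdrawals:

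1. A transaminase above 3 × ULN together with either TBL above 2 × ULN or INR above 1.5.
2. A transaminase above 3 × ULN with a listed clinical feature or eosinophilia above 5%. The 12.8 wording ends "right upper quadrant pain or tenderness, fever, rash, and/or eosinophilia", so eosinophilia is enough by itself.
3. A transaminase above 8 × ULN.
4. A transaminase above 5 × ULN lasting more than 2 weeks.

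The next paragraph of 12.8 opens with "Abnormal values in AST and/or ALT concurrent with abnormal elevations in TBL that meet the criteria outlined above". It then has the Investigator arrange a return visit within 24 to 48 hours "for repeat assessment of ALT, AST, TBL, alkaline phosphatase and gamma glutamyl transferase, detailed history and physical examination", and adds that "if the above transaminase elevation criteria are confirmed by the first set of follow-up laboratory tests, the patient must be withdrawn from the trial". The following paragraph says that a transaminase above 3 × ULN or TBL above 2 × ULN "alone are not considered potential cases of drug-induced liver injury, but will be followed as detailed above, within 72 hours".

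Section 10 is worded differently. Before a liver withdrawal, "the Investigator may choose to confirm the transaminase elevations by repeating the following laboratory tests within 24 to 48 hours", and the tests are "ALT, AST, TBL, INR, % eosinophils, gamma glutamyl transferase and alkaline phosphatase". The synopsis gives the same list. Section 9.1.9 sends Investigators to 12.8 "for guidance on evaluation of potential drug-induced liver injury".

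**The concern.** A rule that makes withdrawal depend on confirmation should name the tests that can confirm it. Section 12.8 defines cases partly by INR and partly by eosinophil percentage, ties withdrawal to the first follow-up laboratory results, and then names a panel with neither test. Section 9.1.9 makes 12.8 the place a site would look when an abnormal liver result comes in, and its repeat is worded as an instruction, whereas Section 10's is optional.

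What is at stake is the decision for an individual patient. A site working from 12.8 could have a patient who qualified through INR or eosinophilia, run every test that 12.8 names, and be unable to say whether the criterion was confirmed.

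**Working it through.** The plan states no figure to reproduce, so the check is a comparison of texts.

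Step 1: the panels, test by test.

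| Repeat test | Section 10 and synopsis | Section 12.8 |
|---|---|---|
| ALT | yes | yes |
| AST | yes | yes |
| TBL | yes | yes |
| Gamma glutamyl transferase | yes | yes |
| Alkaline phosphatase | yes | yes |
| INR | yes | no |
| % eosinophils | yes | no |
| Count | 7 | 5 |

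The difference is 7 − 5 = 2 tests. Section 12.8 names no laboratory test that Section 10 lacks; it adds only a history and a physical examination. Nothing suggests a deliberate alternative panel.

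Step 2: each way of qualifying, against what 12.8 names.

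| Route to a criterion | Can the 12.8 assessment confirm it? |
|---|---|
| Above 3 × ULN with raised TBL | yes |
| Above 3 × ULN with INR above 1.5 only | no |
| Above 3 × ULN with a clinical feature | yes, through history and examination |
| Above 3 × ULN with eosinophilia only | no |
| Above 8 × ULN | yes |
| Above 5 × ULN for more than 2 weeks | yes, the analytes are there |

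The two failing routes belong to criteria 1 and 2. All the laboratory tests these routes need are on the Section 10 list.

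Step 3: which cases the 12.8 repeat paragraph covers. Two readings are open.

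- Broad: all four criteria. The withdrawal clause refers back to the transaminase criteria above it, directly after a list of four, and Section 10 uses nearly the same phrase for all four. The two failing routes in step 2 then matter.
- Narrow: raised-TBL cases only. The sentence before the repeat instruction speaks only of AST or ALT together with TBL. The panel then fits the cases it covers, and INR-only and eosinophilia-only cases fall to Section 10.

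Step 4: what holds on both readings. Isolated elevations are to be followed in the manner already described, which points back to the five-test panel. A patient with ALT or AST above 3 × ULN and nothing else would move into criterion 1 with a new INR above 1.5, or into criterion 2 with a new eosinophilia. Neither change would be seen on that panel.

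**The case against.** The strongest defence is that the protocol has to be read as a whole. Section 10 and the synopsis say a patient meeting any of the four criteria must be withdrawn, and their repeat names both tests within the same 24 to 48 hours. Nothing in 12.8 displaces this or forbids extra tests. Section 9.1.9 also asks for clinically appropriate follow-up of significant results. Section 12.8 itself requires follow-up until abnormalities resolve or return to baseline, which for a raised INR implies measuring it again. This stands, and it limits the consequence: an Investigator who applies Section 10 is covered.

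The second defence is the narrow reading, on which the panel fits its cases. It is a fair reading, so the confirmation problem is conditional. It does not answer step 4 of the working.

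A third is that routine laboratory work already includes prothrombin time and a white-cell differential (Table 9.1.9-1). That helps only at scheduled sampling. From Visit 7 (week 48) onward, scheduled visits are 24 to 28 weeks apart (for example 76 − 48 = 28 and 156 − 132 = 24), so routine sampling does not replace a prompt repeat.

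A reader might also infer two stronger points that the documents do not support.

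- That INR-only or eosinophilia-only patients could properly stay on treatment. They could not, because Section 10 requires withdrawal.
- That a patient above 8 × ULN without raised TBL belongs on the 72-hour path, so that the repeat comes later than the 48-hour limit. This requires ignoring that 12.8 lists above 8 × ULN as a criterion in its own right. An elevation alone most naturally means one that meets none of the listed criteria, and 72 hours is an outer limit in any case.

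**Conclusion.** The text is wrong as written: it is an internal inconsistency in an individual withdrawal rule. The omission of two tests is certain. The inability to confirm an INR-only or eosinophilia-only case depends on the 12.8 paragraph covering all four criteria, which its withdrawal clause favours and its opening sentence does not. The gap in following isolated elevations depends on neither reading.

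The practical size is modest: an unclear withdrawal decision at a site working from 12.8 alone. The documents do not allow the number of affected patients to be derived, and no length of delay should be claimed. Reporting to the sponsor within 24 hours does not depend on confirmation. The SAP's potential Hy's Law table (4.5.3.1) uses only transaminases and bilirubin, so it is unaffected, and no sample size or error rate is involved. It should be corrected because it concerns patient safety and the correction is simple.

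**What to change.** In Protocol 12.8:

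- Add INR and % eosinophils to the repeat panel, so that it matches Section 10 and the synopsis. Keep the history and physical examination.
- Replace "Abnormal values in AST and/or ALT concurrent with abnormal elevations in TBL that meet the criteria outlined above" with wording that covers a result meeting any of the four listed criteria. Without this, the longer panel would still not reach INR-only or eosinophilia-only cases on the narrow reading.
- State that the 72-hour follow-up applies only to elevations meeting none of the four criteria.
- Keep Section 10's option to withdraw without waiting for a repeat, and say in 12.8 that it applies.

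The cost is a few lines of clarification. Both tests are already named in Section 10 and the synopsis, and the routine panel already includes prothrombin time and a differential. One side effect needs a decision: the sentence to be replaced also classes these cases as important medical events, so widening it extends that class to all four criteria. If the sponsor does not intend that, the sentence can be split.

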13 STATISTICAL CONSIDERATIONS

A statistical analysis plan (SAP) will be produced prior to carrying out the database hard lock. Any deviations from the original SAP will be described in the final clinical study report.

13.1 Sample Size, Power and Significance Levels

As this is an open label safety study, there is no formal sample size calculation. All patients who wish to continue on IMP from the populations included in the double-blind Phase 2 and Phase 3 Core Studies in DS and LGS will be eligible for inclusion. Approximately 680 patients will be enrolled.

All data collected during this study will be summarized across time, using appropriate descriptive statistical methods. There will be no formal hypothesis testing.

13.2 Interim Analysis

At least one interim analysis will be conducted to support New Drug Application and Marketing Authorization Application filings. Further interim analyses may be conducted as required.

13.3 Analysis Sets

For this study, there will be only one analysis set:

Safety

All patients who receive at least one dose of IMP in the study will be included. Only patients for whom it has been confirmed that they did not take any IMP will be excluded from this safety analysis set.

13.3.1 Protocol Deviations

Protocol deviations will be listed and reasons for excluding any data from the analysis population will be summarized.

13.4 General Considerations

Unless stated otherwise, continuous variables will be summarized showing the number of non-missing values (*n*), mean, standard deviation, median, minimum and maximum and categorical variables will be summarized showing the number and percentage of patients falling into each category. Summaries will be presented overall as well as for the different etiologies (DS and LGS) separately.

13.5 Accountability and Background Characteristics

13.5.1 Enrollment and Disposition

All patients (screened, enrolled, prematurely terminated IMP) will be accounted for in the enrollment and disposition summary tables.

13.5.2 Baseline and Demographic Characteristics

Age, sex, race (as allowed per local regulations) and any other demographic or baseline characteristics will be summarized, using appropriate summary statistics.

13.5.3 Medical History

Previous and current medical conditions will be summarized by system organ class, including details of the duration of epilepsy, the types of seizures and seizure duration currently experienced by the patients.

13.5.4 Concomitant Medication

Concomitant medications taken 2 weeks prior to and during the study will be summarized separately, by medication class and active ingredients.

13.6 Endpoints and Statistical Methods

13.6.1 Evaluable Period

All data collected during this study will be summarized across time, using appropriate descriptive statistical methods. Where baseline data are available from the Core Studies (such as seizure frequencies, quality of life assessments, Vineland-II, other measures of safety [such as vital signs, clinical laboratory samples]), changes from pre-randomization baseline of the Core Study will also be presented. Treatment compliance and exposure to treatment will also be summarized.

13.6.2 Primary Endpoint(s)

The primary endpoint is the AE profile and other safety assessments reported during the study.

13.6.2.1 Adverse Events

AEs will be coded according to the Medical Dictionary for Regulatory Activities dictionary.

A treatment emergent AE is one that started, worsened in severity or seriousness, following the first dose of IMP in this study. Any AEs that are continuing from the Core Study will be carried over into the OLE study and transcribed in the CRF, only becoming classified as treatment emergent if they worsen.

Descriptive presentations of treatment emergent AEs will be given by preferred term and system organ class for the safety analysis set. The number of patients reporting at least one AE will be provided.

The following summaries will be produced:

- Pre-existing AEs.
- All-causality AEs.
- Treatment related AEs.
- All-causality AEs by severity.
- All-causality serious AEs.
- Treatment related serious AEs.
- AEs reported as leading to permanent cessation of study treatment.
- Fatal AEs.

13.6.2.2 Clinical Laboratory Data

Clinical laboratory data from Central Laboratory obtained at baseline (Core Studies), screening (OLE Visit 1), during treatment and at the end of treatment and the change from baseline (Core Studies), during and at the end of treatment will be summarized for the safety analysis set using appropriate summary statistics. Categorical shift tables will also be presented, showing the numbers of patients with values outside the normal range at each clinic visit.

In order only to confirm normal hepatic function before OLE dosing commences, an additional blood sample may be taken at Visit 1 to analyze ALT, AST, TBL and INR at a local laboratory. These data will only be used for eligibility determination.

13.6.2.3 Vital Signs, 12-lead Electrocardiogram, Physical Examination and Other Safety Data

Vital signs, ECG and physical examination data will be summarized at baseline (Core Studies), screening (OLE Visit 1) and at each time point during the treatment period using appropriate summary statistics. Changes in the vital signs from baseline (Core Studies) during and at the end of treatment will also be summarized. Study Medication Use and Behavior Survey data will be summarized using appropriate summary statistics.

13.6.2.4 Columbia-Suicide Severity Rating Scale Data

C-SSRS data will be summarized at baseline (Core Studies), screening (OLE Visit 1) and at each time point during the treatment period (including the taper period) using appropriate summary statistics. Changes from baseline (Core Studies) during and at the end of treatment will also be summarized.

13.6.2.5 Cannabis Withdrawal Scale and Pediatric Cannabinoid Withdrawal Scale Data

CWS/PCWS data will be summarized at baseline (Core Studies), the OLE end of taper period, 2 weeks after the OLE end of taper period and at OLE follow-up using appropriate summary statistics. Changes from baseline (Core Studies) following cessation of treatment will also be summarized.

